** QUALITY MEASURES **

- Impella Pre-PCI
- Door to Support Time < 90 minutes
- Establish TIMI III Flow
- Right Heart Cath
- Wean off Vasopressors & Inotropes
- Maintain CPO >0.6 Watts
- Improve survival to discharge to >80%

NATIONAL CARDIOGENIC SHOCK INITIATIVE

[contact]

www.henryford.com/cardiogenicshock

NationalCSI - Algorithm - v1.5 - 11/2017

APPENDIX 2

Adoption of the NCSI Treatment Algorithm & Joining the NCSI

Adoption to the NCSI treatment algorithm is completely voluntary. Deviation from the treatment algorithm can occur without consultation of the primary investigators at the discretion of the primary operator. All AMICS patients, including those with treatment algorithm deviation, can be included in the NCSI registry as there is no formal, nationally accepted or standardized protocol or treatment algorithm for treatment of AMICS. Operators and hospitals are encouraged to review the pilot study data and treatment algorithm to determine if they wish to adopt the NCSI treatment algorithm as their standard of care for the treatment of AMICS.

Multi-hospital collaboration is considered a cornerstone to the success of the NCSI. We are reaching out nationally and encouraging hospitals to work together to collect data and demonstrate the success of regional shock protocols and/or treatment algorithms. Hospitals joining the NCSI group voluntarily agree to share data, post-discharge, including demographics, procedural characteristics and outcomes as detailed in the case report form. Data is de-identified and HIPAA-compliant. Data generated from the index procedure admission to discharge (or death, if prior to discharge) will be collected retrospectively and de-identified. Prior to discharge, surviving patients will be asked to consent to the collection of data at 30 days and 1 year post-index procedure. This data collection can occur via follow up phone call, electronic chart review, or any other method that complies with the site's SOPs.

To formally join and affiliate with NCSI, we request the minimum following requirements of the interested hospitals:

1. Implantation of >10 Impella per year (for any indication)

2. Adoption of the NCSI treatment algorithm as standard of care for patients who present with AMICS
3. Identification of a local Primary Investigator (PI) to coordinate data collection

After the above requirements are met, a hospital may request to join NCSI through Henry Ford Hospital's NCSI website (www.henryford.com/cardiogenics shock). The hospital site will be contacted and interviewed by a member of the NCSI team. Once a hospital is accepted to join NCSI, a formal data-use agreement between the institution and Henry Ford Hospital must be completed.

APPENDIX 3

Case Report Form

National Cardiogenic Shock Initiative

Case Report Form

(Version 2.0)

Please complete the entirety of the worksheet. Upon completion, please email this worksheet [SECURE] to: [contact]. Please email/call if there are any questions or concerns.

Demographics

Date of Impella Insertion _____

Implanting Physician _____

Hospital: Name _____

Hospital: City, State _____

Age of Patient _____

Gender (please circle) Male Female

Race (please circle) White Black Hispanic Other

Medical History

Does the patient have a history of Diabetes?	Yes	No	N/A
Does the patient have a history of TIA/CVA?	Yes	No	N/A
Does the patient have a history of ESRD?	Yes	No	N/A
Does the patient have a history of CKD?	Yes	No	N/A
Does the patient have a known LVEF <50%?	Yes	No	N/A
Has the patient had a prior CABG?	Yes	No	N/A
Has the patient had a prior PCI?	Yes	No	N/A
Has the patient had a prior Myocardial Infarction?	Yes	No	N/A

FOR HFH USE ONLY

NCSI #: _____

Admission Characteristics

Was the patient transferred from another hospital?	Yes	No	N/A
If yes, was the patient on support prior to transport?	Yes	No	N/A
What support device was used?	IABP	Other: _____	
Was cardiogenic shock present on admission to your institution?	Yes	No	N/A
Did the patient experience any of the following (prior to arrival in the Cath Lab):			
Anoxic Brain Injury?	Yes	No	N/A
Cardiac Arrest (In Hospital)?	Yes	No	N/A
Cardiac Arrest (Out of Hospital)?	Yes	No	N/A
Did the patient require CPR prior to Impella implant?	Yes	No	N/A
Was the patient undergoing active CPR at the time of Impella implantation?	Yes	No	N/A
Was the patient treated with medically-induced hypothermia?	Yes	No	N/A

**** Important Timings **** Please estimate if exact timings are unavailable.

Please do not leave blank.

Arrival to Hospital (date and time) Date _____ Time _____
Onset of AMI (date and time) Date _____ Time _____
Onset of Shock (date and time) Date _____ Time _____
Time of Impella Insertion (date and time) Date _____ Time _____

Using the above timings, please calculate the following times:

Door to Support Time (minutes): _____

Door to Balloon Time (minutes): _____

Procedural Characteristics (please circle the best choice, if answer is not known please write "N/A")									
Impella Placement:		1. Prior to PCI		2. Post PCI		3. Intra-procedural			
RHC Placement:		1. Prior to Impella		2. Post Impella		3. No RHC obtained			
Impella Used:			Impella Access:			AMI Type?			
2.5 CP 5.0 RP Other: _____			 Femoral  Axillary  Other: _____			STEMI NSTEMI			
PCI Attempted?	TIMI FLOW		Evidence of Thrombus Pre-PCI?	# of Diseased Vessels?	# Vessels Treated?	# of Stents?	Culprit Lesion(s) Location(s)		Other Lesion(s) Location(s)
YES	Pre-PCI	Post-PCI					1. LM	5. Ramus	1. LM 5. Ramus
NO	0	0		0	0		2. LAD	6. SVG	2. LAD 6. SVG
Successful?	1	1	YES	1	1		3. LCx	7. LIMA	3. LCx 7. LIMA
YES	2	2		2	2		4. RCA	8. RIMA	4. RCA 8. RIMA
NO	3	3	NO	3	3				
Access for PCI?	Was complete revascularization performed?		Thrombectomy used?	Atherectomy used?	PCI Complications?  NO  YES				
1. Radial	YES NO		YES NO	YES NO	If YES:  Stent Thrombosis				
2. Femoral	YES NO		YES NO	YES NO	 Evidence of Residual Thrombus				
	YES NO		YES NO	YES NO	 OTHER: _____				
Was patient taking antiplatelet medication at home?  No  Aspirin  Clopidogrel  Ticagrelor  Prasugrel  N/A									
 OTHER: _____									
Was patient loaded with antiplatelet prior to PCI:  No  Aspirin  Clopidogrel  Ticagrelor  Prasugrel  Cangrelor  Abciximab									
 Eftifibatide  Tirofiban  N/A  OTHER: _____									
If oral antiplatelets were given, what route were they given?  By Mouth  NG/OG Tube  Rectal  N/A  Other: _____									
Was the oral antiplatelet crushed?  Yes  No  N/A									
When was antiplatelet administered?  EMS  ER  Pre-PCI  Post-PCI  N/A  Other: _____									
Anticoagulation used during PCI:  Heparin  Bivalirudin  Other: _____									

Please give a brief description of the patient admission: _____

HEMODYNAMIC & LABORATORY VALUES (Pre-procedure & Prior to starting Vasoactive Medications)			
These values should represent the "worst hemodynamics" that demonstrate level of shock			
HR	SBP	DBP	MAP

HEMODYNAMIC & LABORATORY VALUES: (Pre-Impella)								
These values represent the hemodynamics prior to Impella Insertion, at the beginning of the PCI procedure								
HR	SBP	DBP	MAP	Troponin	Cr	AST	Hgb	Lactate
RA/CVP	RV	PA	PCWP	CO  Fick  TD  CCO	CI	CPO	PAPI	LVEDP
PA Sat.	Admission Glucose	VASOACTIVE AGENTS: (DOSE):	Norepinephrine	Dopamine	Epinephrine	Vasopressin	Dobutamine	Milrinone

HEMODYNAMIC & LABORATORY VALUES: Post-PCI, in the Cath Lab (with Impella running)								
These values represent the Cath Lab hemodynamics post PCI, at the end of the procedure								
HR	SBP	DBP	MAP					
RA/CVP	RV	PA	PCWP	CO  Fick  TD  CCO	CI	CPO	PAPI	LVEDP
PA Sat.	VASOACTIVE AGENTS: (DOSE):	Norepinephrine	Dopamine	Epinephrine	Vasopressin	Dobutamine	Milrinone	Other:

HEMODYNAMIC & LABORATORY VALUES: 12 hours Post-Impella Implant (ONLY if Impella is running)								
HR	SBP	DBP	MAP	Troponin	Cr	AST	Hgb	Lactate
RA/CVP	RV	PA	PCWP	CO  Fick  TD  CCO	CI	CPO	PAPI	LVEDP
PA Sat.	VASOACTIVE AGENTS: (DOSE):	Norepinephrine	Dopamine	Epinephrine	Vasopressin	Dobutamine	Milrinone	Other:

HEMODYNAMIC & LABORATORY VALUES: 24 hours Post-Impella Implant (ONLY if Impella is running)								
HR	SBP	DBP	MAP	Troponin	Cr	AST	Hgb	Lactate
RA/CVP	RV	PA	PCWP	CO  Fick  TD  CCO	CI	CPO	PAPI	LVEDP
PA Sat.	VASOACTIVE AGENTS: (DOSE):	Norepinephrine	Dopamine	Epinephrine	Vasopressin	Dobutamine	Milrinone	Other:

POST PROCEDURAL FOLLOW UP

Time & Date of Impella Explant: Time: _____ Date: _____

WEANING OF HEMODYNAMIC SUPPORT:

Support was weaned according to: PA Sat Echo RHC Hemodynamics
 Other: _____

Total hospital duration (Days): _____

Left Ventricle Ejection Fraction (Pre-Impella): _____ (Prior to discharge): _____

DID THE PATIENT SURVIVE THE INDEX PROCEDURE? Yes No N/A

Was the patient transferred to VAD/Transplant Center Yes No N/A

 If "Yes", DID THE PATIENT SURVIVE TO TRANSFER? Yes No N/A

Did the patient have any additional support devices implanted post-index procedure? Yes No N/A

 If "Yes", which device was used: _____

DID THE PATIENT SURVIVE TO DISCHARGE? Yes No N/A

Was the patient discharged to hospice? Yes No N/A

Did the patient experience any significant Impella-related complications?

NO Vascular Complications Hemolysis

OTHER – Please explain: _____

Did the patient require any blood transfusions? No Yes – # of transfusions: _____

Was any external form of vascular bypass performed to provide lower extremity perfusion during Impella (i.e. antegrade access, "up and over" perfusion catheter, etc.)?

No Yes – Please Explain: _____

Please provide a brief description of the patient's hospital course (including significant complications and discharge circumstances):

Please Explain: _____

If the patient did not survive, please indicate the major cause of death (fatal bleeding, anoxic brain injury, worsening cardiogenic shock, patient/family wishes?)

Please Explain: _____

Cardiac Medications on Discharge (name only): _____

- END OF FORM -

APPENDIX 4
Patient Exclusion Form

National Cardiogenic Shock Initiative

PATIENT EXCLUSION FORM

(Version 2.0)

Please complete and email this form via [SECURE] email to: [contact].
Please email/call if there are any questions or concerns.

Hospital: _____

Hospital - City, State: _____

Physician: _____

Date: _____

Age: _____

Gender: Male Female Other

Race: White Black Hispanic Other

Patients will be excluded if there is at least one NO response to the inclusion criteria or at least one YES response to the exclusion criteria.

INCLUSION CRITERIA:

YES NO

- | | | |
|--------------------------|--------------------------|---|
|  |  | ACUTE MI: Symptoms with ECG and/or biomarker evidence of STEMI or NSTEMI |
|  |  | CARDIOGENIC SHOCK: Defined by the presence of at least two of the following: |
| |  | Hypotension: Systolic blood pressure \leq 90mm at baseline, or use of inotropes or vasopressors to maintain SBP \geq 90 |
| |  | Evidence of end organ hypoperfusion (cool extremities, oliguria or anuria, or elevated lactate levels) |
| |  | Hemodynamic criteria: Cardiac index of $<$ 2.2 L/min/m ² or a cardiac power output \leq 0.6 watts. |
|  |  | Patient is supported with Impella |
|  |  | Patient undergoes PCI |

Continued on next page →

FOR HFH USE ONLY

NCSI #: _____

EXCLUSION CRITERIA:

YES NO

- Evidence of Anoxic Brain Injury
- Unwitnessed out of hospital cardiac arrest or any cardiac arrest in which ROSC is not achieved in 30 minutes
- IABP placed prior to Impella
- Septic, anaphylactic, hemorrhagic, and neurologic causes of shock
- Non-ischemic causes of shock/hypotension (*pulmonary embolism, pneumothorax, myocarditis, tamponade, etc.*)
- Active Bleeding
- Recent major surgery
- Mechanical Complications of AMI
- Known left ventricular thrombus
- Patient who did not receive revascularization
- Mechanical aortic valve
- Patient refused to sign consent for 1M & 1Y follow-up

Notes:

Completed by:

SIGNATURE

NAME (PRINTED)

DATE

APPENDIX 5
30 Day Follow-Up Form

National Cardiogenic Shock Initiative
30 Day Follow-Up
(Version 1.0)

Upon completion, please email this form via [SECURE] email to: [contact].
Please email/call if there are any questions or concerns.

NCSI #: _____

Hospital: _____

Hospital - City, State: _____

Date of Impella Implant: _____

Date of Follow-Up: _____

Patient Follow-Up – ≥ 30 Days from Date of Impella Implant:

Did the patient survive to 30 Days?

- YES
- NO
- Unknown
- Patient Unavailable
- Refused
- Other: _____

Point of Contact for Follow-up:

Patient Spouse LAR/Proxy Other: _____

Method of Follow-up:

- Phone Call
- Electronic Medical Record Review (patient signed-in for visit with ID at 30 or more days)
- Mail
- Email
- Other: _____

NOTES: _____

Follow-up performed by: _____

Title: _____

Signature: _____ Date: _____

APPENDIX 6
1 Year Follow-Up Form

National Cardiogenic Shock Initiative

1 Year Follow-Up

(Version 1.0)

Upon completion, please email this form via [SECURE] email to: [contact].
Please email/call if there are any questions or concerns.

NCSI #: _____

Hospital: _____

Hospital - City, State: _____

Date of Impella Implant: _____

Date of Follow-Up: _____

Patient Follow-Up: \geq 365 Days from Date of Impella Implant:

Did the patient survive to 1-year?

- YES
- NO
- Unknown
- Patient Unavailable
- Refused
- Other: _____

Point of Contact for Follow-up:

Patient Spouse LAR/Proxy Other: _____

Method of Follow-up:

- Phone Call
- Electronic Medical Record Review (patient signed-in for visit with ID at 365 or more days)
- Mail
- Email
- Other: _____

NOTES: _____

Follow-up performed by: _____

Title: _____

Signature: _____ Date: _____

National CSI – 1 Year Follow-Up—v1.0 – July, 2018

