From this data, the following Quality Metrics will be tracked:

- Discharge survival
- Duration of shock-to-support times

- Use of Impella Support pre-PCI
- Use of right heart catheter for hemodynamic monitoring
- Attainment of TIMI III flow post reperfusion
- Attainment of Cardiac power > 0.6 watts after completion of therapy
- Reduction or elimination of vasopressors and inotropic agents.

Population and Eligibility Criteria

Due to the heterogeneous cohort of patients who present with AMICS, we have defined a specific subset of patients from whom outcomes are to be collected. Approximately 500 adult patients will be approached to participate in the registry at approximately 75 sites in the United States. The duration of hospital participation in this research study is anticipated to be approximately 3 years.

Registry Inclusion Criteria

1. Symptoms of acute myocardial infarction (AMI) with ECG and/or biomarker evidence of S-T elevation myocardial infarction (STEMI) or non-S-T elevation myocardial infarction (NSTEMI)
2. Cardiogenic shock is defined as the presence of at least two of the following:
 - a. Hypotension (systolic blood pressure ≤ 90 mm Hg, or inotropes/vasopressors to maintain systolic blood pressure ≥ 90 mmHg)
 - b. Signs of end organ hypoperfusion (cool extremities, oliguria or anuria, or elevated lactate levels)
 - c. Hemodynamic criteria represented by a cardiac index of < 2.2 L/min/m² or a cardiac power output ≤ 0.6 watts.

3. Patient is supported with an Impella
4. Patient undergoes PCI

Registry Exclusion Criteria

1. Evidence of Anoxic Brain Injury
2. Unwitnessed out of hospital cardiac arrest or any cardiac arrest in which return of spontaneous circulation (ROSC) is not achieved within 30 minutes
3. IABP placed prior to Impella
4. Septic, anaphylactic, hemorrhagic, and neurologic causes of shock
5. Non-ischemic causes of shock/hypotension (pulmonary embolism, pneumothorax, myocarditis, tamponade, etc.)
6. Active bleeding for which mechanical circulatory support is contraindicated
7. Recent major surgery for which mechanical circulatory support is contraindicated
8. Mechanical complications of AMI (acute ventricular septal defect (VSD) or acute papillary muscle rupture)
9. Known left ventricular thrombus for which mechanical circulatory support is contraindicated
10. Mechanical aortic prosthetic valve
11. Contraindication to intravenous systemic anticoagulation

Risks/Benefits of and Alternatives to Patient Participation

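### The pre-Impella vasoactive row of the case report form has no Other cell, but the three later rows do, so any before-after reduction measure rests on unequal agent lists (minor)

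*Protocol*

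**What the plan says.** The list of quality metrics under Research Procedures includes "Reduction or elimination of vasopressors and inotropic agents". The protocol gives no operational definition of it.

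The data come from the case report form in Appendix 3. Its pre-Impella panel carries the instruction "These values represent the hemodynamics prior to Impella Insertion, at the beginning of the PCI procedure". The agent row of that panel holds PA saturation, "Admission Glucose", the agents and dose label, and then norepinephrine, dopamine, epinephrine, vasopressin, dobutamine and milrinone. It ends there. In the post-PCI, 12-hour and 24-hour panels the list runs "Norepinephrine Dopamine Epinephrine Vasopressin Dobutamine Milrinone Other".

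An earlier panel, headed "Pre-procedure & Prior to starting Vasoactive Medications", asks only for heart rate and systolic, diastolic and mean pressure. A free-text line asks for a short account of the admission and does not mention drugs or doses. Under Data Management, the REDCap database is said to hold only the fields that are on the form.

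**The concern.** A reduction is a change between two times, so both times should be measured with the same list of agents. Here the baseline list is shorter than the later lists. By printing an Other cell three times, the form accepts that agents outside the six may be in use and are worth recording. Nothing in the protocol suggests that they appear only after support has begun.

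One listed quality metric is at stake, together with the stated goal of lowering total use of vasopressors and inotropes. An analysis plan can work around the gap, but it cannot recover a baseline value that the form never requested.

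**Working it through.** **Is the difference real?** Cells in the agent rows, counted from Appendix 3:

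| Row | Cells | Total |
|---|---|---|
| Pre-Impella | PA saturation, admission glucose, label, 6 agents | 9 |
| Post-PCI, 12 h, 24 h (each) | PA saturation, label, 6 agents, Other | 9 |

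The only difference is admission glucose in the first row against Other in the rest. Each row is complete at nine cells, so a cell lost in reading the PDF is unlikely.

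**What is recorded, patient by patient (number of agents, before to after):**

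| Situation | True | Recorded |
|---|---|---|
| Unlisted agent only, continued | 1 to 1 | 0 to 1 |
| Unlisted agent only, stopped | 1 to 0 | 0 to 0 |
| One listed and one unlisted, exactly one stopped | 2 to 1 | 1 to 1 |
| One listed and one unlisted, both stopped | 2 to 0 | 1 to 0 |
| One listed and one unlisted, neither stopped | 2 to 2 | 1 to 2 |

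In the last two rows the reduced or not-reduced status is still right. In the third it is wrong.

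**Illustration of size.** The plan states no figure to reproduce. All inputs here are assumptions:
- a share L = 0.80 of patients is on one listed agent at baseline;
- a share u is on one unlisted agent, independently of the listed one;
- each agent is stopped with probability s, and none is newly started;
- the denominator is patients with any agent at baseline, as recorded or as true.

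The true denominator is D = L + u − Lu. The share of it on both agents is k = Lu/D.

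*Reduction as fewer agents after than before:*
- Recorded: (1 − u)s + u·s² = s − u·s(1 − s)
- True: s + k·s(1 − s)
- Shortfall: (u + k)·s(1 − s)

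For u = 0.05 and s = 0.5: D = 0.80 + 0.05 − 0.04 = 0.81 and k = 0.04/0.81 = 0.0494. Recorded is 0.5 − 0.05 × 0.25 = 48.7%. True is 0.5 + 0.0494 × 0.25 = 51.2%.

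| u | Recorded / true, s = 0.3 | Gap (points) | Recorded / true, s = 0.5 | Gap (points) |
|---|---|---|---|---|
| 0 | 30.0% / 30.0% | 0 | 50.0% / 50.0% | 0 |
| 2% | 29.6% / 30.4% | 0.8 | 49.5% / 50.5% | 1.0 |
| 5% | 29.0% / 31.0% | 2.1 | 48.7% / 51.2% | 2.5 |
| 10% | 27.9% / 32.0% | 4.1 | 47.5% / 52.4% | 4.9 |
| 20% | 25.8% / 34.0% | 8.2 | 45.0% / 54.8% | 9.8 |

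*Elimination as off all agents afterwards:*
- Recorded: s − u·s(1 − s)
- True: s − k·s(1 − s)
- Shortfall: (u − k)·s(1 − s)

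At s = 0.5 the recorded and true values are 48.75% and 48.77% (u = 5%), 47.50% and 47.56% (u = 10%), and 45.00% and 45.24% (u = 20%). The largest gap over the grid is 0.24 points.

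**The case against.** The strongest reply is that the protocol never defines the metric as a comparison of the pre-Impella panel with the later ones. The algorithm's quality measures and its explantation criteria speak of weaning off all agents. That is an end state, readable from the later panels, and all of those have an Other cell. The definition may stand in an analysis plan that is not shown. This stands, and it is why the point is limited to before-after measures. It does not remove the point, because the metric names reduction as well as elimination, and reduction needs a baseline.

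The form also records dose, so a count of agents is not the obvious definition. That stands too, and the 1 to 10 points belong to the agent-count definition only. An unlisted agent has no baseline dose either, so a dose total over all agents would have the same gap.

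A reader might infer that every patient on an unlisted agent is misclassified, for example 25 to 50 of 500 at an assumed 5% to 10%. The documents do not support this. With one listed and one unlisted agent, the reduction status is wrong only when exactly one is stopped. That has probability 2s(1 − s), which is 42% at s = 0.3 and 50% at s = 0.5. The 500 is also the number to be approached, not the number enrolled.

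A reader might also infer that each lost patient pushes the metric the same way. A patient on an unlisted agent alone leaves the recorded denominator whether the agent is continued, which raises the proportion, or stopped, which lowers it.

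Finally, the baseline is not wholly without a place for the agent, since a site may write it in the admission description. That text is optional in content and hard to analyse.

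**Conclusion.** The point holds as a minor data-capture defect. The form requests less about vasoactive agents at baseline than afterwards, and no structured field makes up the difference.

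Its effect is confined to change-from-baseline measures within one descriptive quality metric. Under an agent-count definition the net error understates reduction, so it runs against the treatment algorithm and would not create a favourable result. The gap is 0.8 to 9.8 percentage points for assumed unlisted use of 2% to 20%, given 80% of patients on one listed agent, independence, stopping probabilities of 0.3 or 0.5 and no new starts. None of these rates comes from the protocol, so the true size is unknown, and it may be zero. An off-all-agents measure moves by at most 0.24 points on the same assumptions. Survival to discharge, 30 days and 1 year is unaffected.

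The stronger reading, that the metric as a whole is distorted, would need a definition and a frequency of unlisted agents that the documents do not give.

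**What to change.** Add an Other cell, with name and dose, to the pre-Impella vasoactive row of the form and the database, so that all four panels carry the same list. For patients already entered, send sites one query for any unlisted agent in use at Impella insertion. Index-admission data are taken retrospectively from medical records, so the answer should usually be retrievable. Until this is done, compute any change from baseline on the six common agents at every time point, and say so where it is reported.

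The cost is one extra field, a one-off query and an interim metric that is slightly less complete.

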Prior to discharge from the cath lab, a formal neurovascular check should be performed for assessment of Impella-related limb ischemia. This can be performed either by an in-depth physical examination, peripheral angiogram, or lower extremities doppler studies. If signs of limb ischemia are noted, the peel-away sheath should be removed (if not already done so) with reassessment. If limb ischemia persists, antegrade access should be performed to provide distal lower extremity blood flow.

4. Post-PCI Hemodynamics

After the intervention is completed, right heart pressures, cardiac output, and CPO will be obtained. If CPO is > 0.6 , no further intervention is required. If CPO is ≤ 0.6 , right heart pressure will be reviewed to identify evidence of right ventricular failure if present (PAPi < 0.9).

If evidence of right ventricular failure are present (PAPi < 0.9), or if the Impella is suctioning, operators should consider right ventricular support with commercially available devices (Impella or Tandem Heart). Irrespective of CPO, evidence of RV shock is a warning not

to increase alpha agonists. These agents dramatically increase pulmonary vascular resistance (PVR) at a time of minimal RV reserve and can cause a lethal spiral as increasing doses of alpha agonists to maintain arterial pressure leads to decrease forward RV flow and worsens hypotension.

If CPO < 0.6 persists and RV shock is not the cause, consideration for the placement of an Impella 5.0 or a durable left ventricular assist device (LVAD) should be considered.

5. Weaning and Explantation

Impella devices should only be considered for explantation once the following criteria have been met:

1. Weaning of all inotropes and vasopressors
2. CPO > 0.6 watts without vasopressors or inotropes, and
3. PAPI > 0.9.

6. Safety and Monitoring

Cautious attention should be paid to the infrequent yet serious complication of limb ischemia with the use of large bore sheaths and devices. Detailed neurovascular checks should be performed while on Impella support. Use of antegrade sheaths to provide flow to the affected limb is strongly recommended in such cases. Prophylactic use antegrade access may also be considered, especially in patients who will likely require >24 hours of support. Although rare hemolysis can also occur, daily hemoglobin level should be obtained while on support. If there are signs of hematuria, Impella positioning should be checked via echocardiography.

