- Prior to discharge from the Cath Lab, a detailed vascular exam should be performed including femoral angiogram and Doppler assessment of the affected limb.
- If indicated, external bypass should be performed.

ICU Care

- Daily hemodynamic assessments should be performed, including detailed vascular assessment
- Monitor for signs of hemolysis and adjust Impella position as indicated

Device Weaning

Impella should only be considered for explantation once the following criteria are met:

- Weaning off from all inotropes and vasopressors
- CPO >0.6, and PAPI > 0.9

Bridge to Decision

Patients who do not regain myocardial recovery within 3-5 days, as clinically indicated, should be transferred to an LVAD/Transplant center. If patients are not candidates, palliative care options should be considered.

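### The CRF's device-complication item counts only events the site calls significant and Impella-related, bleeding has no box of its own, and hemoglobin stops at 24 hours, so device-complication and bleeding rates may be understated

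*Protocol*

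**What the plan says.** In Appendix 3, under the post-procedural follow-up, the form asks "Did the patient experience any significant Impella-related complications". The tick boxes run "NO Vascular Complications Hemolysis", followed by an other option with free text. The protocol does not define what makes a complication significant or what makes it Impella-related.

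The same form collects related information in five other places:
- a "PCI Complications" item among the procedural characteristics, with boxes for stent thrombosis, residual thrombus and other;
- "Did the patient require any blood transfusions", with the number of transfusions;
- a yes/no question on external bypass to perfuse the leg, with an explanation;
- a free-text hospital course that asks for significant complications;
- a free-text cause of death, whose examples begin "fatal bleeding, anoxic brain injury, worsening cardiogenic shock".

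Hemoglobin appears in three laboratory panels: before Impella, at 12 hours, and in the last one, "24 hours Post-Impella Implant (ONLY if Impella is running". Appendix 1, section 6 (Safety and Monitoring) says that a "daily hemoglobin level should be obtained while on support". It also speaks of patients likely to need more than 24 hours of support. The Bridge to Decision box on the algorithm card concerns "Patients who do not regain myocardial recovery within 3-5 days", who should be transferred.

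**The concern.** The item applies two filters before an event is counted, and each of about 75 sites sets both for itself. The hazards that the protocol itself recognises are not matched by fields. Appendix 1 has large-bore access and systemic anticoagulation precede Impella insertion and singles out limb ischemia for monitoring. The eligibility criteria exclude active bleeding and contraindications to anticoagulation. The cause-of-death line names fatal bleeding first. Yet non-fatal bleeding has no event box, and limb ischemia shares one with every other vascular complication.

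At stake is what a published complication rate would mean. The registry is single-arm, and Analysis and Publication of Data foresees publication of all data. A reader would take a complication rate as the rate in supported patients. What the form delivers is the rate of events that sites chose to attribute to the device. An analysis plan cannot repair this later, because Data Management limits the database to the fields on the form and the two follow-up forms ask only about survival.

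**Working it through.** The protocol states no complication rate, so there is no figure to reproduce. The check compares what the form can yield with what a complication rate needs.

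**1. Direction of the filter.** Let A be all events of a given kind between insertion and discharge, S those the site calls significant, and R those it calls Impella-related. The item counts A ∩ S ∩ R, which can never exceed A. Against an all-cause count, the error therefore runs one way. Against a count of events truly caused by the device it could run either way, since a site can over-attribute as well as under-attribute.

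**2. Size.** Reported rate = all-cause rate × share captured. The protocol gives neither factor, so no figure follows from it.

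**3. Whether the other items restore the count.**

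| Item | What it adds | What it leaves out |
|---|---|---|
| PCI complications | A second place for procedural events, with free text | No bleeding or access-site box |
| Transfusions | Bleeding that led to transfusion, with no attribution filter and no 24-hour limit | Non-transfused bleeding; no date or cause, so bleeding and hemolysis are not separated |
| External bypass | Treatment of a threatened limb | Appendix 1, section 6 allows prophylactic antegrade access, so a yes does not identify ischemia; untreated ischemia is missed |
| Hospital course | Events without device attribution | Still limited to significant events, undefined; free text that must be coded |
| Cause of death | Fatal events | All non-fatal events |

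Two gaps remain in structured form: non-transfused bleeding, and limb ischemia as distinct from other vascular events.

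**4. Hemoglobin.** The form has values before Impella, at 12 hours and at 24 hours. The algorithm recommends daily values while support lasts and foresees support beyond 24 hours. For a patient still supported after 24 hours, a later fall leaves no value in the database unless the site describes it in text or records a transfusion.

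**5. Sites.** Population and Eligibility Criteria gives approximately 500 patients at approximately 75 sites: 500 / 75 = 6.7 patients per site. Site-level rates would be very imprecise on any form, so the pooled rate is the more important casualty.

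**6. Link to the objectives.** Seven quality metrics are listed for tracking. None is a complication or bleeding rate.

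**The case against.** The strongest reply is that this is a registry, not a treatment study, and that it collects more on safety than the one item suggests. A bleed that the site blames on the device can go under other. One blamed on the PCI has the other line of the PCI item. A significant one belongs in the narrative, and a transfused one in the transfusion count. All of that is correct. A reader might infer that the device item is the only place where complications enter the form, and the form itself shows otherwise. It is only the sole device-complication item.

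Two further inferences are tempting and fail. The first is that most of the support period goes unobserved because support lasts 3 to 5 days. That interval is the time by which patients without recovery should be transferred. It is not a support duration. The card allows removal in the cath lab, and no typical duration is stated. The second is that the form contradicts the algorithm on hemoglobin. The daily value is a bedside recommendation in an algorithm from which operators may deviate (Appendix 2), and a registry need not abstract every value that is measured.

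It is also fair to say that no complication rate is a tracked metric and that no per-site comparison of complications is planned. This lowers the priority. It does not remove the point: the sponsor chose to collect device complications, and any rate reported from them would carry both undefined filters.

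**Conclusion.** The point holds in a limited form. The device-complication count is filtered by two undefined site judgements. Non-transfused bleeding and limb ischemia have no structured field of their own, and recorded hemoglobin ends at 24 hours even when support continues. Device-complication and bleeding rates may therefore be understated against an all-cause count and may not be comparable across sites.

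The documents do not support saying that the rates will be understated by a given amount, or that they will differ by site. Both would need capture fractions that the protocol does not give. The conclusion assumes that sites receive no definitions outside this document and that free text is not systematically coded. If either is done, the problem shrinks. Because the tracked metrics are not affected, this is an inexpensive improvement of lesser priority.

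**What to change.** Reword the item in Appendix 3 to: *Did any of the following occur from Impella insertion to discharge, whatever the cause?* Give a yes/no box and a date for each of limb ischemia, other vascular complication, bleeding, hemolysis and other, and state on the form the definition of bleeding to be used. Keep *related to Impella in the site's judgment* as a second column, so that the attributed rate can still be reported beside the all-cause rate.

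Add one laboratory field: the lowest hemoglobin between insertion and explant, with its date, taken from the chart. The explant date and time are already on the form. This value will not separate bleeding from hemolysis, but it gives a laboratory check that does not end at 24 hours.

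The change concerns data capture only and leaves patient care untouched. It costs the revision of one CRF page with the matching database fields, and slightly more abstraction time per patient. Complication rates will look higher than under the present item, and a report should say why.
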